## 5.2.2 Clinical Laboratory Tests

Some laboratory parameters will be collected by central and local laboratories. In the cases where a visit's sample is collected on both central and local labs, the central lab result will be presented in the TLF.

Laboratory values outside the reference range will be identified in listings, using flags to identify whether above or below the range limits. Chemistry, Hematology, Coagulation, Urinalysis, and Cytometry results will be presented separately. Laboratory parameters used for pharmacokinetic and pharmacodynamic purposes will be presented separately (see Section 5.3 below).

Listings of all lab results and out of range lab results with their corresponding changes from baseline will be presented. Baseline will be considered as the pre-dose measure on Study Day 1, or the screening assessment if missing the Study Day 1 assessment.

A table of descriptive statistics will be presented for chemistry, hematology, coagulation, urinalysis, and cytometry laboratory results by randomized dose level and by cohort. The number and percent of subjects with low, normal, and high assessments at each scheduled visit will be tabulated by randomized dose level and by cohort.

## 5.2.3 Vital Signs

The listing of vital sign data will include change from baselines. Baseline will be considered the Study Day 1 pre-dose assessment, or the screening assessment if missing the Study Day 1 assessment. In the listing, data fulfilling the following criteria will be flagged:

Value	Parameter	Low	High
Observed	Systolic Blood Pressure	$\leq$ 80	≥165
	(mmHg)		
	Diastolic Blood Pressure	$\leq$ 40	≥95
	(mmHg)		
	Pulse (bpm)	$\leq 40$	≥120
	Temperature (°C)		≥38

\*mmHg=millimeters of mercury, bpm=beats per minute, °C=degrees Celsius

A table of descriptive statistics will be presented for each vital sign parameter by randomized dose level and by cohort. The number and percent of subjects with low, normal, and high assessments at each scheduled visit will be tabulated by randomized dose level and by cohort.

### 5.2.4 Electrocardiogram (ECG)

The listing of ECG data will include change from baselines. Baseline will be considered the Study Day 1 pre-dose assessment, or the screening assessment if missing the Study Day 1 assessment.

ECG results will have an overall interpretation and will be classified as normal or abnormal, with the abnormal further classified as either not clinically significant (NCS) or clinically significant (CS). Abnormalities will be documented by the investigator in the eCRF. This information will be included in listings.

Value		Parameter	I	[.ow	High
vuite		Turumeter	-	Low	ingi
Observed		QT, Bazett's	QT		≥450
		Correction (QT	cB),		
		Fridericia's	QT		
		Correction (Q7	ГcF)		
		(msec)			
		PR (msec)	<	≤100	≥240
		QRS (msec)			≥140
		Heart Rate (bpm)	<	≤40	≥120
Increase fro	om	QT, QTcB, Q	TcF		≥30
baseline		(msec)			

Further, in the listing, data fulfilling the following criteria will be flagged:

Version 1.0

\*msec=milliseconds

A table of descriptive statistics will be presented for each ECG parameter by randomized dose level and by cohort. The number and percent of subjects with low, normal, and high assessments and change from baseline at each scheduled visit will be tabulated by randomized dose level and by cohort.

#### 5.2.5 Physical Examination

Physical examination data will be summarized in listing(s).

## 5.3 Exploratory Efficacy and Pharmacodynamic Analyses

While the primary objective of this study is safety, exploratory efficacy and pharmacodynamic analyses will be presented. All efficacy analyses will be evaluated on the Intent-to-Treat Set and Per Protocol Set. All pharmacodynamic analyses will be evaluated on the PD Set and Per Protocol Set.

## 5.3.1 Red Blood Cell (RBC) Transfusions

The absolute and change in number of RBC transfusions per month will be tabulated using descriptive statistics by randomized dose group, by cohort, by phase of the study (Baseline, Part A Core Study Phase and Part B Long Term Extension Phase) and over the whole on-treatment study parts (Part A and Part B combined).

Summary statistics will be presented by study phase as follows:

- Baseline:
  - Number of Transfusions and Units per month for the *n* subjects who had at least 1 infusion in the 365 days prior to first study dose
  - Number of Transfusions and Units per month for the N subjects in the dose group (i.e. all subjects in the dose group, regardless of receiving transfusions prior to enrollment)
- Post-Baseline Study Phases (Part A, Part B, Part A and B combined):
  - Number of Transfusions and Units per month for the *n* subjects who had at least 1 infusion in the respective phase
  - Number of Transfusions and Units per month for the N subjects in the dose group (i.e. all subjects in the dose group, regardless of receiving transfusions during the respective phase)
  - Change from Baseline of the Number of Transfusions and Units for the N subjects in the dose group (i.e. all subjects in the dose group, regardless of receiving transfusions during the respective phase)

Only whole blood and Packed Red Blood Cell (PRBC) transfusions will be included.

The number of RBC transfusions per month will be calculated for each part of the study as:

RBC transfusions per month

number of transfusion reported during study part \* 28 number of days in that part of study

The whole on-treatment study will be from first dose to last dose received. A similar calculation will be used for the number of units transfused per month.

The baseline number of transfusions per month will be calculated as number of transfusions reported on 12-month transfusion history /12.

All 12-month transfusion history and on study transfusion data will be listed by Cohort. A separate listing of the number of transfusions per month and number of units transfused per month for baseline, each part and over the whole on-treatment study parts will also be included.

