## Planned Dose Level

Planned doses through the Part A Core Study Phase (screening to Day 336) will be as follows:

	Cohort 1 wAIHA N= up to 12	Cohort 2 CAD N= up to 12
Group 1	Daily SC doses of 270 mg for 12 months (n= up to 6)	Daily SC doses of 270 mg for 12 months (n= up to 6)
Group 2	Daily SC doses of 360 mg for 12 months (n= up to 6)	Daily SC doses of 360 mg for 12 months (n= up to 6)

Following Month 12 and the completion of the Part A Core Study Phase, subjects will be eligible to participate in Part B, a Long-term Extension Phase, in order to continue to receive treatment with APL-2. During the Part A Core Study Phase this study will utilize an acetate buffered mannitol formulation of APL-2 (for the 270 mg/d and 360 mg/d doses). During the long-term extension phase, subjects will transition to APL-2 doses of 1,080 mg twice weekly, and may transition to 1,080 mg every three days (ie, a dose on every third day) if necessary.

Note: Some subjects may complete the Part A Core Study Phase prior to the availability of the acetate buffered sorbitol formulation. These subjects will continue with their 270 mg/d or

360 mg/d doses using the mannitol formulation until the acetate buffered sorbitol formulation is available.

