# 11.3.2 Planned Dose Levels and Dosing Schedule

Starting on Day 1 (Visit 2), subjects will receive SC APL-2 daily for up to 336 days at the corresponding dose.

Planned doses will be as follows:

	Cohort 1: wAIHA (n=12)	Cohort 2: CAD (n=12)
Group 1	Daily SC doses of 270 mg for 12 months (n=6)	Daily SC doses of 270 mg for 12 months (n=6)
Group 2	Daily SC doses of 360 mg for 12 months (n=6)  Daily SC doses of 360 mg for 12 months	

Subjects in each cohort will be randomly (1:1) assigned to receive either APL-2 270 mg/d or APL-2 360 mg/d at Day 1, and will continue treatment through Day 336 (Part A, the Core Study Phase).

The first SMC meeting will be scheduled once 4 enrolled subjects complete 28 days of dosing (or at an earlier time point in order to review subject data), and subsequent SMC meetings will be held at 6-month intervals throughout the study.

A. At Visit 15 (Day 336) and the conclusion of Part A, subjects are eligible to continue to receive treatment with APL-2 through Part B, the Long-Term Extension Phase. These subjects should not complete follow-up procedures but will continue participation in the study indefinitely until the subject discontinues or the development program is terminated. Section 17.3 provides information on the conduct of the Long-Term Extension Phase.

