### 3.3 Study Design

This is a Phase II, open-label, prospective pilot study of APL-2 conducted in subjects with a primary diagnosis of wAIHA or CAD in parallel. The study will consist of up to 24 subjects, a target of 12 subjects with a primary diagnosis of wAIHA in Cohort 1 and a target of 12 subjects with a primary diagnosis of CAD in Cohort 2. Subjects will be randomized 1:1 to a 270mg or 360mg daily SC APL-2 dosage group within each cohort for up to 12 months (Part A, the Core Study Phase).

Following Day 336 and the completion of the Part A Core Study Phase, subjects will be eligible to participate in Part B, a Long-Term Extension Phase, in order to continue to receive treatment with APL-2. The Long-Term Extension Phase is described later in this section.

Through Part A (Day 336), dose escalation from 270 mg/d to 360 mg/d, or deescalation from 360 mg/d to 270 mg/d may occur after a thorough evaluation of available safety and laboratory assessment.

Safety will be assessed throughout the study; serial blood and urine samples will be collected for these assessments. Blood samples will be collected for the assessment of APL-2 PK. Additional samples for assessment of PD will also be collected.

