#### 3.3.1 Sample Size Considerations

As this is a pilot study the sample size is not based on formal statistical testing. The sample size is considered sufficient to obtain useful safety, tolerability, PD, and PK data to assist the planning of future studies.

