## 4.3 Test Hypothesis and *P*-Value Justification

No formal inferential statistics will be applied to data collected in this study.

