#### 5.3.1.4 Transfusions Summary Tables

The following tabular summaries will be prepared:

- Part A + B PRBC: Summary statistics will be prepared by Cohort (Cohort 1 wAIHA / Cohort 2 CAD) for the ITT Set and Per Protocol Set who have Part A + B Baseline or at least one post-Part A + B Baseline PRBC transfusion during Part A + B phase:
  - Part A + B Baseline Transfusions Per Month
  - Part A + B Transfusions Per Month
  - Part A + B Baseline Units Per Month
  - Part A + B Units Per Month
- Part B PRBC: Summary statistics will be prepared by Cohort (Cohort 1 wAIHA / Cohort 2 CAD) for the ITT Set and Per Protocol Set who have Part B Baseline or at least one post-Part B Baseline PRBC transfusion during Part B Phase:
  - o Part B Baseline Transfusions Per Month
  - o Part B Transfusions Per Month
  - o Part B Baseline Units Per Month
  - o Part B Units Per Month

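### Per-subject transfusion rates are averaged with equal weight whatever the exposure, so in a group of 6 one transfused early stopper can inflate the mean several-fold; an exposure-weighted rate should stand beside it.

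*SAP*

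**What the plan says.** Part A SAP 5.3.1 plans the summary as follows: "The absolute and change in number of RBC transfusions per month will be tabulated using descriptive statistics by randomized dose group". It sets the rate: "The number of RBC transfusions per month will be calculated for each part of the study as" the count in the part × 28, divided by the days in that part. The rates are summarised for the transfused subjects and for all N subjects in the dose group, and they are also listed. Section 5 of that SAP fixes the statistics as n, mean, SD, median and range. Baseline is the 12-month transfusion history divided by 12.

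The ITT set (4.2) takes anyone with one dose, with no minimum exposure. Efficacy is repeated in the Per Protocol set (5.3), which is limited to subjects who complete Visit 15.

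On design: "Subjects will be randomized 1:1 to a 270mg or 360mg daily SC APL-2 dosage group within each cohort". The Protocol synopsis plans up to 6 subjects per dose group in each cohort, and Protocol 11.3.2 says "subjects will receive SC APL-2 daily for up to 336 days".

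Part B SAP 5.3.1 uses the same kind of per-subject rate, and 5.3.1.4 says "Summary statistics will be prepared by Cohort (Cohort 1 wAIHA / Cohort 2 CAD) for the ITT Set and Per Protocol Set", separately for Part A + B and for Part B.

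Neither SAP plans a rate of total transfusions over total time. Part A SAP 5.3.1 does not say how many days a subject who stops early contributes to Part A. It gives first-to-last-dose wording only for the whole on-treatment period.

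**The concern.** A subject treated for 14 days carries the same weight in the mean as one treated for 336. Over a short denominator one transfusion becomes a large monthly rate: 2 in 14 days is 4.0 per month. With at most 6 subjects per dose group, that single value can set the group mean. Every baseline rate rests on 12 months of history, so change from baseline sets a fairly stable number against one that may rest on two weeks.

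The number of transfusions is a listed efficacy endpoint, and these tables are meant to inform later development. A reader who takes the mean as the group's transfusion burden per month of treatment could be seriously misled.

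**Working it through.** The documents give no transfusion rate to reproduce, so this is direct arithmetic on the SAP's formula.

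**Inputs from the documents.** Group size m = 6 (Protocol synopsis, upper limit); full Part A exposure 336 days (Protocol 11.3.2); 28-day scaling and equal weight (Part A SAP 5.3.1 and 5).

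**Assumptions.** One subject stops on day d after k transfusions. The other five are treated for 336 days with b transfusions each. Days run to the last dose.

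**Formulas.**
- Planned mean = [k × 28/d + 5 × b × 28/336] / 6
- Rate per treated 28 days = 28 × (k + 5b) / (5 × 336 + d)
- With b = 0 the ratio is (1680 + d) / (6d), whatever k is

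**Only the stopper transfused (b = 0).**
- Day 14, k = 2: mean (2 × 28/14)/6 = 0.667; pooled 56/1694 = 0.0331; ratio 1694/84 = 20.2.
- Day 28, k = 1: mean (1 × 28/28)/6 = 0.167; pooled 28/1708 = 0.0164; ratio 1708/168 = 10.2.
- Other stop days: 40.2 (Day 7), 5.2 (Day 56), 3.5 (Day 84), 1.8 (Day 168).
- Solving d = 1680/(6f − 1), a ratio f of 10 needs a stop by about Day 28 and a ratio of 20 by about Day 14.

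**Others also transfused (k = 1).**

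| Transfusions in the other five | Day 14 | Day 28 |
|---|---|---|
| None | 20.2 | 10.2 |
| One in total | 10.5 | 5.5 |
| One each | 4.1 | 2.4 |
| Two each | 2.6 | 1.7 |
| Four each | 1.8 | 1.3 |

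**If the stopper's 84 follow-up days count as Part A days (b = 0).** Day 14: 1778/(6 × 98) = 3.0. Day 28: 1792/(6 × 112) = 2.7.

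**Quiet early stopper.** With a common rate r in the other five and none in a Day-14 stopper, the planned mean is 5r/6 = 0.833r and the pooled rate is 1680r/1694 = 0.992r. The mean is about one-sixth lower.

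**Bias or noise.** Assume Poisson counts at one common rate r, with stopping unrelated to that rate. Both summaries then have the same expectation.
- Variance of the planned mean: r × (28/d + 5/12)/36, which is 0.0671r at Day 14 and 0.0394r at Day 28.
- Variance of the pooled rate: 28r/(1680 + d), which is 0.0165r and 0.0164r.
- SD ratio: about 2.0 and 1.5.

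In 200,000 simulated groups at each of five rates from 0.05 to 1 per 28 days, a ratio of 10 or more arose in at most about 0.5% of groups with any transfusion.

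**What the planned tables would show in the Day 14, k = 2 case.** Mean 0.67, median 0, maximum 4.0; the transfused-only row 4.0 from one subject; Per Protocol mean 0. None of these is the 0.033 per treated month.

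**The case against.** The strongest reply has four parts.

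1. **Visibility.** Median, range and per-subject listings are already planned, so a mean of 0.67 with median 0 and maximum 4.0 gives the outlier away. This stands, and it lowers the stakes. It does not supply the missing rate; the Per Protocol repeat removes the early stopper rather than weighting that subject.

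2. **Low stakes.** "No formal inferential statistics will be applied to data collected in this study", and "As this is a pilot study the sample size is not based on formal statistical testing". Efficacy is labelled exploratory, and no between-dose difference is specified for transfusions. This stands too.

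3. **The pooled rate is a different quantity.** It gives a Day-14 treatment failure 14/1694 = 0.8% of the weight. Take one subject with 24 baseline transfusions (24/12 = 2.0 per month on the Part A SAP formula) who stops on Day 14 after 1 (also 2.0), and five with none before or after. The planned mean change is 0, which is right. A pooled on-study rate of 28/1694 = 0.0165 against an equally weighted baseline of 2.0/6 = 0.333 would show a 95% fall with no true change. This stands, and it rules out using the pooled rate as the headline.

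4. **The denominator.** Part A SAP 4.5 keeps all data for subjects who discontinue in Part A. If the follow-up days count, the ratio is about 3. This stands as a reason to define the days.

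A reader might infer that 10- to 20-fold inflation is typical, or that early stoppers distort the mean equally in both directions. The documents support neither. The large ratios need a sole transfused subject who stops in the first four weeks, and a quiet stopper lowers the mean by only about one-sixth.

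**Conclusion.** The point holds as a cheap improvement to a descriptive analysis. The planned mean weights subjects equally whatever their exposure, and no exposure-weighted rate accompanies it. In a group of 6, one transfused early stopper can inflate the mean several-fold. The 10- to 20-fold figures assume that this subject is the only one transfused, stops on Day 14 to 28, and has days counted to the last dose. The documents do not forecast any of these. With one transfusion in every subject the ratio is about 2 to 4.

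If stopping is unrelated to transfusion need, the cost is extra variability (SD about 2.0 or 1.5 times that of the pooled rate), not bias. A link is plausible: Protocol 12.8 allows withdrawal for adverse events and severe laboratory abnormalities, and Part A SAP 5.2.1 lists haemolysis as an event of special interest. The documents do not establish one.

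A reader might extend the point to everything in the Part B SAP. That goes too far. Its ITT set contains only subjects who rolled over after Part A and received 1080 mg, so a 14- or 28-day denominator cannot arise in Part A + B. It can arise in Part B alone, after a stop soon after the first 1080 mg dose. The size there is not computed, because the documents do not give the group sizes or lengths of follow-up.

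**What to change.** In Part A SAP 5.3.1, and for Part B alone in Part B SAP 5.3.1.4:

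- Beside the planned mean and median, add for each group and part 28 × (sum of transfusions) / (sum of days at risk), and the same for units.
- State which days an early stopper contributes, and count that subject's transfusions over exactly the same period.
- For the comparison with baseline, weight each subject's baseline rate by that subject's on-study days: Σ(baseline rate × days) / Σ(days). In the example under objection this gives 2.0 × 14/1694 = 0.0165 on both sides, and the false reduction disappears.
- Keep the per-subject summary as the headline and keep the listings as planned.

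Summed exposure is not new to the sponsor: Part B SAP 5.2.1.4 already divides by total time at risk for adverse-event incidence.

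**Cost.** A few table rows and one definition, from data already collected, with no change to conduct. The downside is that the pooled rate down-weights early treatment failures and can be dominated by one long-stay, heavily transfused subject. Both summaries should therefore be shown.

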The use of silica reagents in coagulation panels should be avoided. Apellis previously conducted an investigation into prolonged activated partial thromboplastin time (aPTT) observed in subjects treated with APL-2. It was confirmed that false positive aPTT prolongation occurred when coagulation panels were performed using a Stago Analyzer and, specifically, silica reagents. It was determined that there was interference between the silica reagents and PEGylated APL-2, resulting in artificially prolonged aPTT.

Details regarding the dosing regimen and administration of APL-2 are provided in Section 11 (Part A) and Section 17.3.4 (Part B). Subjects should be instructed to take their APL-2 treatment as prescribed, and to contact the investigator immediately for guidance in the event of any missed doses. In subjects with PNH, discontinuation with APL-2 or noncompliance with the

prescribed dose regimen has been observed to lead to the potential for an increased risk for serious hemolysis. The Sponsor's medical monitor should be contacted before interrupting or discontinuing treatment with APL-2.

There is a potential health benefit for trial participants from receipt of study drug. At the proposed dose levels of APL-2, a significant decrease in complement-mediated hemolytic activity was observed in all APL-2-treated subjects (both treatment-naïve and treated previously with eculizumab) in PNH Phase 1 studies and in HV studies. APL-2 may, therefore, reduce complement-mediated hemolytic activity in AIHA patients. In this context, a careful evaluation of the risk/benefit ratio should be made. APL-2 at the proposed doses has been deemed safe for up to 9 months of administration in preclinical studies and 28 days in HV studies. In addition, in studies of subjects with PNH (See Section 6.2), ongoing treatment with APL-2 270 mg/d or 360 mg/d has been well-tolerated for at least 2 months, and has provided clinical benefit to subjects either treated alone or as an add-on to eculizumab.

If efficacious and safe, APL-2 is expected to continue to improve Hb levels and reduce transfusion dependency in these patients throughout the Part A treatment period of 336 days (the Core Stud Phase) and beyond (through the Part B Long-Term Extension Phase).

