### 3.2.2 Efficacy Endpoints

- Change from baseline in hemoglobin
- Number of red blood cell (RBC) transfusions during the study
- Change from baseline in absolute reticulocyte count
- Change from baseline in lactate dehydrogenase (LDH)
- Change from baseline in haptoglobin
- Change from baseline in indirect bilirubin

- APL-2 serum concentrations and PK parameters, as appropriate
- Change from baseline in Functional Assessment of Chronic Illness Therapy (FACIT) scale and the Linear Analog Scale Assessment scale (LASA) including energy level, ability to perform daily activity, and overall quality of life (QoL)

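### Part A SAP 5.3.1: the transfused-subject rows cover different subjects at baseline and in Part A, so read against each other they understate a reduction and, when response is uneven, can show no fall or a rise

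*SAP*

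**What the plan says.** The number of RBC transfusions is a listed efficacy endpoint (Part A SAP 3.2.2: "Number of red blood cell (RBC) transfusions during the study"). Protocol 7.3 states the hoped-for benefit: if efficacious and safe, "APL-2 is expected to continue to improve Hb levels and reduce transfusion dependency in these patients".

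Part A SAP 5.3.1 tabulates transfusions and units per month by randomized dose group and cohort, in three kinds of row:

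- **Transfused-subject (n) rows.** At baseline, the "subjects who had at least 1 infusion in the 365 days prior to first study dose". After baseline, the "subjects who had at least 1 infusion in the respective phase". I read infusion here as transfusion.
- **All-subject (N) rows.** At baseline and in each phase; after baseline these are for "all subjects in the dose group, regardless of receiving transfusions during the respective phase".
- **Change row.** "Change from Baseline of the Number of Transfusions and Units for the N subjects in the dose group". No change is planned for the n subjects.

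The baseline rate is "number of transfusions reported on 12-month transfusion history /12". The on-study rate is the count times 28, divided by the "number of days in that part of study". Each subject's rates are also listed. Section 4.3 rules out formal inference.

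**The concern.** The two n rows share a label and will sit in one table as Baseline and Part A, which invites a before-and-after reading. They do not describe the same people. The baseline set is fixed before dosing. The Part A set is defined by the result being summarised, so a complete success is removed from the average. The Part A n row also cannot reach zero: one transfusion over a full Part A is already 28/336 = 0.083 per month.

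The study is descriptive, with up to 6 subjects per dose group in each cohort, so the tables are the result. No planned row follows the subjects transfused at baseline, who are the ones able to show reduced dependency. No count of those who become transfusion-free is planned either.

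**Working it through.** The documents give no transfusion figures to reproduce. Subject-level counts and response patterns below are assumptions. The formulas, the group size of 6 and the 336 days come from the plan.

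**Formulas.** Baseline rate = 12-month count / 12. Part A rate = count × 28 / 336.

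**Why the n rows diverge.** Let n_b be the number transfused at baseline and n_s the number transfused in Part A. If nobody is newly transfused on study, the total transfused is the same whichever row is used and only the divisor differs:

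n-row ratio (Part A / baseline) = ratio in the baseline-transfused subjects × n_b / n_s

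Every subject freed lowers n_s and inflates the n-row ratio. The row fails to fall once the true ratio reaches n_s / n_b. In the same situation the all-N ratio equals the ratio in the baseline-transfused subjects, because subjects at zero in both periods scale both means equally.

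**Worked examples, one dose group of 6 (assumed counts).**

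| Baseline counts | Part A counts | n rows | Baseline-transfused set, zeros kept | All-N rows |
|---|---|---|---|---|
| 2,2,3,3,4,12 | 0,0,0,0,0,11 | 0.361 (n=6) to 0.917 (n=1), +153.8% | 0.361 to 0.153, -57.7% | 0.361 to 0.153, -57.7% |
| 0,0,3,3,4,12 | 0,0,0,0,0,11 | 0.458 (n=4) to 0.917 (n=1), +100.0% | 0.458 to 0.229, -50.0% | 0.306 to 0.153, -50.0% |
| 4,4,4,4,4,4 | 0,0,0,0,0,4 | 0.333 (n=6) to 0.333 (n=1), 0.0% | 0.333 to 0.056, -83.3% | 0.333 to 0.056, -83.3% |
| 4,4,4,4,4,4 | 0,0,0,0,0,2 | 0.333 (n=6) to 0.167 (n=1), -50.0% | 0.333 to 0.028, -91.7% | 0.333 to 0.028, -91.7% |

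Check on the first row: 26/12/6 = 0.361; 11 × 28/336 = 0.917; 0.917/6 = 0.153; 0.153/0.361 = 0.423; 0.423 × 6/1 = 2.54, a rise of about 154%.

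**How often.** Simulated groups of 6, with Poisson counts, gamma-distributed rates, about two thirds transfused at baseline, mean 0.5 per 28 days, the SAP's /12 baseline, and groups where both n rows exist:

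- *Uneven response (60% freed, the rest unchanged).* The n row fails to fall in about 42 to 43% of groups, the baseline-transfused set in about 6 to 12%, and the all-N row in about 6 to 13%. In roughly 8 to 22% of groups the Part A n row is empty.
- *Uniform response (every rate cut by 50 to 90%).* The n row fails to fall in about 1 to 8%. A second run with a mean of 4 transfusions a year gave 0.3 to 11%. There the median n-row ratio was 0.24 to 0.28 for a true ratio of 0.10, and 0.55 to 0.56 for a true ratio of 0.50: a fall, but too small.
- *Who is freed matters.* In that second run, freeing the 4 or 5 lightest users of 6 made the n row fail to fall in 82 to 85% of groups. Freeing 4 or 5 at random gave 38 to 41%.

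**A side effect of the formulas.** Baseline uses a calendar month and on-study a 28-day month, so an unchanged rate reads 12 × 28/365 = 0.921, a 7.9% fall. This partly offsets the n-row bias, touches the all-N rows too, and is a separate matter.

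**The case against.** The strongest reply is that the plan already answers the question. The all-N rates keep the zeros, and the only change from baseline is calculated on all N subjects. In every example above the all-N percentage fall equals that of the baseline-transfused set, and in simulation the two fail to fall about equally often. The plan never subtracts one n row from the other. The n is printed, so a drop from 4 to 1 is visible, and each subject's rates are listed. Efficacy is exploratory and no error rate is involved. All of this stands, and it limits the point to two rows of one table.

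Four stronger readings are tempting, and none is supported:

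- *The plan hides the treatment effect.* It does not, because the all-N rows and their change row show it.
- *Only non-responders are averaged on study.* Anyone with at least one Part A transfusion stays in, including a large partial responder or a newly transfused subject. A lightly transfused new subject could even pull the row down.
- *The row will usually point the wrong way.* That needs uneven response. Under a uniform cut it normally still falls.
- *The final analysis has the same fault.* Part B SAP 5.3.1.4 uses one set, transfused at baseline or on study, on both sides for Part B and for Part A + B.

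The later SAP does not cure the Part A table. Its ITT Set is limited to subjects who rolled over and received 1080 mg (4.1), its tables are by cohort (5), and its Introduction says the Version 1.0 SAP produced the Part A analysis. Nor does N minus n give the number freed, since it also counts subjects who were never transfused.

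**Conclusion.** The point holds for the Part A transfused-subject rows. By definition they compare different subjects, and the on-study set is selected on the outcome. When subjects are freed and nobody is newly transfused, the pair understates the reduction by the factor n_b / n_s. Whether it goes as far as no fall or a rise depends on how response is spread: about 42 to 43% of dose groups under the assumed all-or-none pattern, about 1 to 8% under a uniform 50 to 90% cut. Those percentages rest on transfusion rates and response patterns that are not in the documents; the incomparability of the rows does not. The consequence is a misleading pair of rows for a named efficacy endpoint, beside sound rows that show the right answer.

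**What to change.** In the Part A table of SAP 5.3.1:

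1. Replace the post-baseline n row by transfusions and units per month, with change from baseline, in the subjects who had at least one RBC transfusion in the 365 days before first dose, counting on-study zeros.
2. Add the number and percentage of those subjects who are transfusion-free in Part A.
3. Count separately any subject untransfused at baseline who is transfused on study.
4. Keep the all-N rows as the main summary. The baseline-transfused subset is picked for having been transfused, so it is open to regression to the mean and may fall somewhat without any drug effect.

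The cost is SAP wording and one revised table shell. The 12-month history and on-study transfusions are already collected and listed, so this can also be added as a supplementary table. The downside is small subsets within each dose group, which the planned n rows already have.
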